#### Table TTT. Glycemia over Time

### 13 Pharmacokinetics Analyses

Pharmacokinetics analysis will be done on the PK population.

Blood samples for placebo will not be analyzed by the bioanalytical laboratory except for 2 samples per participant receiving placebo, 1 pre-dose and the other at 12h post-dose, to confirm that these participants did not receive liraglutide. These results will be listed in section 16.2 of the CSR.

The placebo group will not be presented in the TFL of this section. In summary tables, only the columns corresponding to the doses will be presented (no "pooled" column).

In this section only, the treatment groups will show the real dose administered, in case the real dose is not one of the scheduled ones.

#### 13.1 Endpoints

The endpoints are:

- Plasma concentration of Liraglutide following a single IA injection at D1 (pre-injection T0-15 min), and 2, 4, 8, 12, 16 and 24 hours post-injection.
- The PK parameters Cmax, Tmax, AUC0-t and T1/2.

#### 13.2 Plasma Concentration of Liraglutide

A summary table will be produced by timepoint:

#### Table TTT. Plasma Concentrations over Time

The plasma concentrations over time will be plotted for each subject, on both arithmetic and logarithmic scales. There will be one series of figures for all subjects at a given dose.

Figure FFF. Plasma Concentrations over Time by Subject - Dose

Figure FFF. Plasma Concentrations over Time by Subject - Dose

Figure FFF. Plasma Concentrations over Time by Subject - Dose

Figure FFF. Plasma Concentrations over Time by Subject - Dose

#### 13.3 Computation of PK Parameters

In case of missing concentration, the individual figure of PK concentrations of the subject will be reviewed, and a decision will be made:

- interpolate the concentration or not
- possibly invalidate some PK parameters (set them to missing)

Concentrations BLOQ will be set to zero if measured at baseline, to LLOQ/2 otherwise.

The parameters will be derived as follows:

- Cmax Maximum concentration achieved computed as max(C0-C6)
- Tmax Time to reach maximum concentration computed as first time Ti where Concentration = Cmax

- AUC0-t The area under the concentration vs. Time curve computed as follows:
  - Tlast = last time where Clast > BLOQ
  - AUC0-t = sum of AUCs using linear trapezoidal summation from time 0 to Tlast
- λz terminal elimination rate constant

computed as follows:

- select the timepoints t1 = T0+16h and t2 = T0+24h, with respective concentrations C1 and C2
- if either concentration is missing,  $\lambda z$  is missing
- otherwise, compute the slope of the line ln(C1) to ln(C2)
- if the slope is negative,  $\lambda z = -slope$
- otherwise λz is missing
- $T1/2 = In(2) / \lambda z$

The dose-normalized parameters Cmax and AUCO-t will also be computed (Cmax/Dose and AUCO-t/Dose).

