#### 6.2 Final Analyses and Reporting

All final, planned, analyses identified in the protocol and in this SAP will be performed only after the last patient has completed the study. A data review meeting will be held prior to database lock and completion of the final analyses.

In addition, no database may be locked, or analyses completed until this SAP has been approved.

Key statistics and study results will be made available following database lock and prior to completion of the final clinical study report (CSR).

Any, post-hoc, exploratory analyses completed to support planned study analyses, which are not identified in this SAP, will be documented and reported in appendices to the CSR. Any results from these unplanned analyses will also be clearly identified in the text of the CSR.

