### 9.2 Methods for Withdrawals, Missing Data, and Outliers

Missing data will not be replaced. Analyses will be done on the maximum available observed data. If a PK point is missing at time t, an interpolation may be done, depending on data review.

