### 9.4 Derived and Computed Variables

For any variable, the baseline value is defined as the last observation before IMP injection.

The time will be split into 3 periods (epochs):

- before treatment (screening)
- during treatment (from IMP injection to 7 days after IMP injection date)

after treatment

The following PK parameters will be calculated from measured plasma concentrations for each participant:

- Maximum observed concentration (Cmax)
- Time of maximum observed concentration (Tmax)
- Area under the curve (AUC0-t)
- Terminal Half-life (T1/2)

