### 13.4 Reporting of PK Parameters

The PK parameters will be summarized. In addition to standard univariate statistics, the coefficient of variation, geometric mean and geometric standard deviation will be added.

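### SAP 13.3 lets an imputed 24 h value into the half-life slope, so a participant quantifiable at 16 h but BLOQ at 24 h is given a half-life of at most 8 h

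*SAP*

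**What the plan says.** SAP 13.3 fixes the handling of values below the quantification limit: "Concentrations BLOQ will be set to zero if measured at baseline, to LLOQ/2 otherwise". For λz it directs the analyst to "select the timepoints t1 = T0+16h and t2 = T0+24h, with respective concentrations C1 and C2". λz is set to missing in only two situations: one of the two concentrations is missing, or the log-linear slope is not negative. Half-life is ln2/λz.

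The same section ends AUC0-t at the last time with a concentration above the limit, so trailing BLOQ values do not enter the AUC.

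Case review is provided for missing values. SAP 13.3 says "In case of missing concentration, the individual figure of PK concentrations of the subject will be reviewed, and a decision will be made", and the possible outcomes include invalidating a parameter. SAP 9.2 says "If a PK point is missing at time t, an interpolation may be done, depending on data review". Neither mentions BLOQ values.

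Protocol 8.4.3 and SAP 9.4 list half-life among four PK parameters; SAP 9.4 calls it "Terminal Half-life". Protocol 10.1.3 and SAP 13 have PK results summarised by dose, and SAP 13.4 adds: "In addition to standard univariate statistics, the coefficient of variation, geometric mean and geometric standard deviation will be added".

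**The concern.** An imputed value is not a missing value, so neither exit from the λz calculation catches it. When 16 h is quantifiable and 24 h is BLOQ, the slope is always negative and a half-life is always produced. That number depends only on how far C16 lies above the assay limit. It carries almost no information about the participant's elimination, yet it enters the summary for the dose level with nothing in the table to mark it.

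The section is also inconsistent with itself. For this participant the last quantifiable time is 16 h. AUC0-t stops there, while λz uses the imputed point after it.

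Plasma PK is the only secondary objective. The secondary endpoint in Protocol 3.2.2 is the plasma concentration; half-life is derived from it.

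**Working it through.** The plan states no figure derived from this rule, so there is none to reproduce.

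**Inputs**
- Post-dose BLOQ value = LLOQ/2; slope from 16 h and 24 h, 8 h apart (SAP 13.3).
- Reference half-life about 13 h after subcutaneous dosing (Protocol 2.1, PK Data). Its use for intra-articular dosing is my assumption; I also show 10 h and 16 h.
- Assessment window ±10 min (Protocol 1.2.2).
- LLOQ and dose levels are not visible. LLOQ cancels out of the limit below.

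**The rule:** T½ = 8 ln2 / ln(C16/C24).

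**The three patterns that contain a BLOQ value**
1. Both BLOQ: LLOQ/2 against LLOQ/2, slope zero, λz missing.
2. 16 h BLOQ, 24 h quantifiable: slope positive, λz missing.
3. 16 h quantifiable, 24 h BLOQ: C24 = LLOQ/2, so T½ = 8 ln2 / ln(2·C16/LLOQ). Since C16 ≥ LLOQ, the denominator is at least ln2 and T½ ≤ 8 h.

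**Values in pattern 3** (8 ln2 = 5.545)

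| C16/LLOQ | ln(2·C16/LLOQ) | Reported T½ |
|---|---|---|
| 1.0 | 0.693 | 8.0 h |
| 1.1 | 0.788 | 7.0 h |
| 1.25 | 0.916 | 6.1 h |
| 1.53 | 1.118 | 5.0 h |

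If actual times were used, the interval could run from 7 h 40 min to 8 h 20 min, and the limit from 7.7 to 8.3 h.

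**Range for a given true half-life T, absorption complete by 16 h.** A BLOQ value at 24 h requires C16 < LLOQ·2^(8/T). The lowest reported value is therefore 8 ln2 / [ln2·(1 + 8/T)] = 8T/(T + 8):
- T = 10 h: 80/18 = 4.4 h
- T = 13 h: 104/21 = 5.0 h (C16 between 1 and 1.53 × LLOQ)
- T = 16 h: 128/24 = 5.3 h

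The upper end is 8 h in each case. With both samples quantifiable and a true 13 h, the rule returns 13.0 h.

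**Effect on a dose group.** Suppose one of six active participants is affected and the other five are at 13 h. The arithmetic mean is (65 + 4.95)/6 = 11.7 h to (65 + 8)/6 = 12.2 h. The geometric mean is 13·(4.95/13)^(1/6) = 11.1 h to 13·(8/13)^(1/6) = 12.0 h.

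**How low exposure must be.** In a one-compartment model with first-order absorption and true 13 h, pattern 3 requires a sampled peak of 1.75 to 3.14 × LLOQ for Tmax 2 to 4 h, and 1.04 to 1.85 × LLOQ for Tmax 8 to 12 h. Over true values of 10 to 16 h the limits are 1.59 to 4.40 and 1.04 to 2.09 × LLOQ.

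**The case against.** The strongest objection is that the pattern may never occur. Nothing in the documents places any cohort in the narrow band of exposure required. The band also narrows as Tmax moves later. Protocol 10.1.1 ties the second placebo sample to the expected time of Cmax, and SAP 13 sets that sample at 12 h, so a Tmax near 12 h is a reasonable inference, though it is not stated. To illustrate, assume a median half-life of 13 h, log-SD 0.3 for half-life and 0.4 for exposure, and an LLOQ at 10, 20 or 30% of the typical sampled peak. The share affected is then 0.2, 3.5 and about 12% for Tmax 8 h, and 0.01, 0.4 and 2.8% for Tmax 12 h. This objection stands: frequency is unknown and may be nil.

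Second, an affected value could be found. SAP 13.2 says "The plasma concentrations over time will be plotted for each subject, on both arithmetic and logarithmic scales", concentrations and parameters are listed, and "A data review meeting will be held prior to database lock and completion of the final analyses". This stands in part. A careful reader could trace the value, but none of these steps carries a BLOQ rule, so whoever noticed it would have to decide ad hoc.

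Third, if Tmax is late, residual absorption matters more. In the same model with true 13 h and both samples quantifiable, the 16–24 h slope returns 14.3, 17.4 and 23.4 h for Tmax 8, 10 and 12 h. That is a separate limitation of the two-point slope. It acts in the opposite direction and the present fix does not address it.

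A reader might infer that the study's half-life is capped at 8 h. It is not: the limit applies to one participant at a time, and only in pattern 3.

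**Conclusion.** The rule is wrong as written for one pattern. With 16 h quantifiable and 24 h BLOQ, the reported half-life cannot exceed 8 h at nominal times, and lies between 5.0 and 8.0 h if the true value is 13 h and absorption is complete. The limit itself follows from SAP 13.3 alone; the 5.0 h end rests on the 13 h assumption.

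The point is minor. Half-life is descriptive with no test or decision attached, and Cmax, Tmax, AUC0-t, the safety analyses and the MTD do not use λz. A reader might also infer that a group mean is materially distorted. The documents do not support that, because the number of affected participants cannot be derived from them.

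**What to change.** Add to SAP 13.3: *Imputed BLOQ values are not used for λz; if the 16 h or 24 h concentration is BLOQ, λz and T½ are set to missing (not estimable).* Only the 24 h case changes a result. Give the number not estimable by dose level in the PK parameter table. This brings λz into line with the AUC0-t rule. Relabelling the parameter as an apparent half-life (16–24 h) is optional.

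The cost is one sentence, one condition in the code and one row in a table. The statistical price is that half-life is reported for fewer participants, and those excluded tend to have shorter half-lives or lower exposure, so the summary of the rest is biased upward. As a small example, take three participants with C16 = 1.6 × LLOQ and true half-lives of 10, 13 and 16 h. Their 24 h values are 0.92, 1.04 and 1.13 × LLOQ, so only the first is BLOQ, and the rule gives that participant 5.545/ln 3.2 = 4.8 h. The true geometric mean is (10·13·16)^(1/3) = 12.8 h. The current rule gives (4.77·13·16)^(1/3) = 10.0 h and exclusion gives (13·16)^(1/2) = 14.4 h. Across a population, under the assumptions given in the objection, the two biases are of about the same size and opposite in sign. The gain is therefore valid individual values and an exclusion that is counted, not a less biased group mean.

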#### PK Set

The PK set will consist of all participants who receive study drug and have at least 1 measurable plasma concentration.

Blood samples for placebo will not be analyzed by the bioanalytical laboratory except for 2 samples per participant receiving placebo, 1 predose and the other around the expected time at which Cmax occurred (as emerging from the actual measurement of the samples of the first dose group) to ensure from a safety perspective that no additional participants could have been on active treatment.

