### 8 Analysis Populations

The following analysis populations are defined for the study:

- Safety population: The safety analysis set will consist of all participants who are enrolled and received 1 dose of study drug.
- PK population: The Pharmacokinetics (PK) analysis set will consist of all participants who receive study drug and have at least 1 measurable plasma concentration. Placebo subjects will not be part of the PK population.

Unless otherwise stated, all analyses will be done on the Safety population.

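### AUC0-t/Dose can cover different time spans across participants and dose levels, because each AUC stops at that participant's own last quantifiable sample and no common-window AUC is defined

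*SAP*

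**What the plan says.** SAP 13.3 sets the end of the AUC in two lines: "Tlast = last time where Clast > BLOQ" and "AUC0-t = sum of AUCs using linear trapezoidal summation from time 0 to Tlast". The same section fixes the value of unquantifiable samples: "Concentrations BLOQ will be set to zero if measured at baseline, to LLOQ/2 otherwise". After Tlast that LLOQ/2 value has no role in the AUC, because the summation has already ended.

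SAP 13.3 then adds: "The dose-normalized parameters Cmax and AUCO-t will also be computed". SAP 13.4 summarises the PK parameters descriptively, with geometric mean and geometric SD, and SAP 13 gives one column per dose. Protocol 8.4.3 lists AUC0-t among the parameters; neither document defines AUC0-24.

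For a missing concentration, SAP 13.3 provides for review of the individual curve, possible interpolation, and possible setting of parameters to missing, without a criterion.

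The PK population in SAP 8 must "have at least 1 measurable plasma concentration", as in Protocol 10.1.1 (PK Set). The documents do not say that the number excluded under this rule will be reported by dose.

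**The concern.** Dividing by dose puts the dose levels on one scale, so a reader of the PK table will look along the row for a trend. That reading assumes the numerator covers the same interval throughout. Here the interval depends on quantifiability, which itself depends on dose. If some low-dose participants are BLOQ at 24 h and no high-dose participants are, AUC0-t/Dose is lower at the low dose only because the integration stopped sooner. That would look like exposure rising more than in proportion to dose. The secondary objective is plasma PK across escalating doses, so an artefact that tracks dose matters even in a descriptive table.

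**Working it through.** The plan states no AUC, LLOQ or Tlast, so there is no figure to reproduce. The check applies the SAP 13.3 rule to model profiles.

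**Inputs**
- Sampling at 0, 2, 4, 8, 12, 16 and 24 h (Protocol 3.2.2).
- Half-life about 13 h (Protocol 2.1, PK Data, subcutaneous route), so k = ln 2 / 13 = 0.0533 per h. That it also holds after intra-articular dosing is an assumption.
- Six active participants per cohort (SAP 7).
- Assumed: one compartment, first-order absorption, Tmax 4, 8 or 12 h. The LLOQ is not given, so results are expressed through Cmax/LLOQ.

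**Profiles.** C(t) is proportional to exp(-kt) - exp(-ka·t), with ka chosen to give the Tmax, scaled to Cmax = 1.

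| Tmax | ka (per h) | C12 | C16 | C24 | AUC0-16/AUC0-24 | AUC0-12/AUC0-24 |
|---|---|---|---|---|---|---|
| 4 h | 0.695 | 0.707 | 0.571 | 0.373 | 0.764 | 0.603 |
| 8 h | 0.243 | 0.929 | 0.796 | 0.540 | 0.708 | 0.519 |
| 12 h | 0.123 | 1.000 | 0.958 | 0.756 | 0.644 | 0.441 |

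Example, Tmax 4 h: the trapezoids are 0.871 + 1.871 + 3.740 + 3.153 + 2.556 = 12.19 to 16 h, plus 8 × (0.571 + 0.373)/2 = 3.776 for the last interval, total 15.97. The ratio is 12.19/15.97 = 0.764.

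**Loss per participant stopping at 16 h:** 1 - 0.764 = 24% to 1 - 0.644 = 36%.

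**Effect on a cohort mean.** With m of six stopping at 16 h, the ratio is 1 - (m/6)(1 - r). For m = 1 this is 0.961 to 0.941, a fall of about 4 to 6%. For m = 3 it is 0.882 to 0.822, a fall of 12 to 18%.

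**When BLOQ truncation occurs.** Tlast is below 24 h when C24 is below the LLOQ, that is when Cmax/LLOQ is below 1/C24: 1/0.373 = 2.7 (Tmax 4 h), 1/0.540 = 1.9 (8 h), 1/0.756 = 1.3 (12 h). Stopping as early as 12 h requires Cmax/LLOQ below 1/C16: 1.75, 1.26 and 1.04. The largest losses therefore need the narrowest margins.

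**What LLOQ/2 at 24 h recovers.** Take the true 24 h value just below the LLOQ, so that C24/2 replaces C24. The lost area is 8 × (C24/2)/2 = 2 × C24.
- Tmax 4 h: 0.746/15.97 = 4.7%, leaving 0.95.
- Tmax 12 h: 1.512/19.26 = 7.9%, leaving 0.92.

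The shortfall falls from 24–36% to about 5–8%.

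**A limit of this check.** At Tmax 12 h with the LLOQ that high, the 2 h and 4 h samples (0.391 and 0.658) could also be BLOQ. Setting both to 0.378 reduces the first three trapezoids from 0.391 + 1.049 + 3.182 = 4.622 to 0.378 + 0.756 + 2.622 = 3.756. That is a further 0.866/19.26 = 4.5% under the present rule and the proposed one alike.

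**The case against.** **AUC to the last quantifiable sample is a usual parameter and is the one the protocol names.** That stands, and it is why AUC0-t should stay. The gap is in dose-normalising it without a common-window companion.

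**The documents lean against frequent truncation.** The half-life is about 13 h against 24 h of sampling, and Protocol 4.3 reports similar systemic exposure by the two routes in dogs. Protocol 10.1.1 says the placebo check sample is to be timed near the Cmax measured in the first dose group, and SAP 13 puts it at 12 h. This suggests measurable levels in that group, though it is an inference. It stands as a reason to treat the effect as conditional.

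**Missing samples already have a rule.** This stands in part. SAP 13.3 allows the AUC to be set to missing, and the 24 h sample falls within the hospital stay. But the choice is made case by case, and a missing last sample has no later value to interpolate towards.

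**Other outputs are unaffected.** Cmax/Dose does not depend on Tlast, and concentrations are summarised by timepoint and plotted by participant. A reader might infer that AUC0-t/Dose is the plan's only view of dose proportionality. It is not, and neither document states a proportionality objective or test.

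**The PK population.** A reader might also infer that dropping one all-BLOQ participant of six inflates the mean by 6/5 = 1.20, and that the population should be redefined. The 20% treats that participant's AUC as zero. Under LLOQ/2 it is 0.5 × LLOQ over 0–2 h plus 22 × 0.5 × LLOQ over 2–24 h, or 11.5 h × LLOQ. With lognormal Cmax, an assumed CV of 50% and Tmax 12 h, the retained mean is 1.13 times the mean of all at a geometric-mean Cmax/LLOQ of 1.5, 1.05 at 2 and 1.01 at 3. This bias also runs opposite to truncation. Including all-BLOQ participants would depart from the protocol's PK set and give them parameters determined by the assay. They would have no Tlast in any case, and they remain traceable in Listing 16.2.18, which uses the Safety population.

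**Conclusion.** The point holds in conditional form. SAP 13.3 lets the integration interval vary between participants and then divides by dose, and nothing in the plan equalises or reports the intervals. Where a participant stops at 16 h, AUC per unit dose is 24 to 36% too low relative to 0–24 h, and one such participant of six moves the cohort mean by about 4 to 6%.

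These sizes rest on the one-compartment model, the subcutaneous half-life and the assumed Tmax range. Whether the effect occurs rests on an LLOQ that the documents do not give, or on a missing 24 h sample whose AUC is kept. The documents do not support saying that AUC0-t/Dose will be distorted, nor that the PK population definition must change, nor that a purely descriptive plan needs a dose-proportionality model.

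**What to change.** In SAP 13.3:
- Add AUC0-24, by the linear trapezoidal rule over the scheduled samples, and make it the AUC that is dose-normalised and summarised across dose levels.
- Use the SAP's existing LLOQ/2 value for a BLOQ 24 h sample.
- Set AUC0-24 to missing if the 24 h sample is absent.
- Keep AUC0-t as a reported parameter, as the protocol specifies.

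In SAP 13.4, report by dose the number of participants with Tlast below 24 h and the number of active participants excluded from the PK population because every sample was BLOQ. Leave the PK population definition as it is.

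The cost is a few lines of SAP text and code, with no new data. The drawback is a small imputed area where the 24 h sample is BLOQ, with AUC0-24 understated by about 5 to 8% when the true value is just below the LLOQ. If all samples are present and quantifiable, AUC0-24 and AUC0-t coincide.

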#### PK Data

In human, after a single subcutaneous (SC) administration (current authorized route of administration) liraglutide is well absorbed from the injection site. Overall bioavailability following SC administration is estimated to be 55% in human. The distribution volume is low and close to plasma volume, which indicates that a high fraction of liraglutide is circulating in plasma. Liraglutide is extensively bound to plasma protein (>98%).

The mean clearance following subcutaneous administration of a single dose liraglutide is approximately 1.2 l/h with an elimination half-life of approximately 13 hours.

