## 3.2.2 Secondary endpoint

• Plasma concentration of liraglutide following a single IA injection. PK samples: D1 preinjection (T0-4h) and 2, 4, 8, 12, 16 and 24 hours post injection.

Plasma concentrations will be performed by

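### The SAP takes the terminal half-life from fixed 16 h and 24 h samples without checking that absorption has ended, so a late Tmax can give a mislabelled, inflated T1/2

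*SAP*

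**What the plan says.** Protocol 3.2.2 and SAP 13.1 give the same post-dose sampling times: "2, 4, 8, 12, 16 and 24 hours post injection". There is also one pre-dose sample, and nothing is drawn for PK after 24 h.

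SAP 13.3 fixes the points for λz for every participant: "select the timepoints t1 = T0+16h and t2 = T0+24h, with respective concentrations C1 and C2". There are two exits. λz is missing "if either concentration is missing", and it is missing when the line through the two log concentrations does not fall. Otherwise T1/2 = ln 2 / λz. The section sets no condition relative to Tmax, no minimum number of points and no check of fit. It does allow individual curves to be reviewed and parameters to be invalidated, but only where a concentration is missing.

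SAP 9.4 lists the result as "Terminal Half-life", SAP 13.3 calls λz the terminal elimination rate constant, and the abbreviation lists of both documents define T1/2 as the elimination half-life.

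Two other places bear on where Tmax may fall. Protocol 10.1.1 (PK Set) places the placebo check sample "around the expected time at which Cmax occurred", to be learned from the first dose group. SAP 13 fixes the placebo samples as "1 pre-dose and the other at 12h post-dose". The only half-life in either document is the subcutaneous one in Protocol 2.1 (PK Data): "elimination half-life of approximately 13 hours".

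**The concern.** A slope is terminal only once input has become negligible. If the joint is still releasing drug between 16 h and 24 h, that input props up the 24 h concentration, the slope is too shallow and T1/2 is too long. The rule neither prevents this nor flags it. With Tmax at 16 h, one of the two points is Cmax itself. With Tmax at 12 h, these are the only two samples after the peak, so nothing can show whether the decline is log-linear.

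T1/2 is one of four derived parameters serving the secondary objective, in the first human use of this route. A participant or dose level with a later Tmax would look as if it eliminated the drug more slowly. With 6 active participants per cohort and arithmetic means in the table, one nearly flat slope can dominate a dose group. Participants whose segment is flat or rising drop out, and in the absence of error these are the slowest absorbers, so the remaining values are also selected.

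**Working it through.** The documents give no figure for T1/2 or Tmax after intra-articular injection, so there is nothing to reproduce. The check applies the SAP rule to an assumed profile.

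**Inputs**
- Sampling times 2, 4, 8, 12, 16 and 24 h (Protocol 3.2.2, SAP 13.1).
- Rule: SAP 13.3, equivalent to T1/2 = 8 × ln 2 / ln(C16/C24).
- Elimination half-life 13 h (Protocol 2.1, subcutaneous), used as a working value. Then ke = ln 2 / 13 = 0.0533 per h, and the last sample is at 24/13 = 1.85 half-lives.
- Assumed: one compartment and first-order absorption, C(t) ∝ exp(−ke·t) − exp(−ka·t), with ka solved from Tmax = ln(ka/ke)/(ka − ke).

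**Check of the formula.** For a pure mono-exponential decline with a 13 h half-life, C24/C16 = 0.653 and the rule returns 13.0 h. Any error therefore comes from absorption continuing after 16 h.

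**One case in full, Tmax 12 h.** ka = 0.1229 per h. C16 ∝ 0.2862 and C24 ∝ 0.2258, so C24/C16 = 0.789 and ln(C16/C24) = 0.237. T1/2 = 8 × 0.693 / 0.237 = 23.4 h, which is 1.80 times 13 h.

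**By true Tmax, no assay error**

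| Tmax (h) | ka (per h) | C24/C16 | T1/2 from rule (h) | Ratio to 13 h |
|---|---|---|---|---|
| 8 | 0.2428 | 0.679 | 14.3 | 1.10 |
| 10 | 0.1682 | 0.727 | 17.4 | 1.34 |
| 12 | 0.1229 | 0.789 | 23.4 | 1.80 |
| 14 | 0.0932 | 0.852 | 34.7 | 2.67 |
| 16 | 0.0727 | 0.911 | 59.3 | 4.56 |

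**By observed Tmax.** The SAP's Tmax is a sampling time, so each observed value covers a span of true peaks. Observed 8 h covers about 5.7 to 9.8 h and gives ratios of 1.01 to 1.31. Observed 12 h covers about 9.9 to 13.9 h and gives 1.3 to 2.6. Observed 16 h covers about 13.9 to 19.7 h and gives 2.6 upwards without a useful limit. At observed 24 h the slope is not negative and T1/2 is already missing.

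**Sensitivity to the model.** With true half-lives of 10 to 15 h, the ratio is 2.16 to 1.66 at Tmax 12 h and 5.9 to 4.1 at Tmax 16 h. With zero-order input ending at 8, 12 or 16 h, the rule returns 13.0 h and there is no bias.

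**Sensitivity to assay error.** The documents give no precision, so 5%, 10% and 15% independent error per concentration are assumed. For true Tmax 12 h, T1/2 is missing in about 0%, 5% and 13% of simulated participants. The 5th to 95th percentiles of the rest are about 16 to 46 h, 12 to 107 h and 9 to 141 h.

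**Would a third point help?** A log-linear fit to 12, 16 and 24 h gives 15.2 h at Tmax 8 h (fixed pair 14.3 h), 19.0 h at true Tmax 9.8 h, which the grid records as 8 h (fixed pair 17.0 h), and 28.6 h at 12 h (fixed pair 23.4 h). The added point is closer to absorption and raises the bias.

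**Does a Tmax gate hold?** Without error, an observed Tmax of 8 h or earlier limits the ratio to 1.31. With error, some late absorbers pass. In 200,000 simulated profiles with true Tmax 12 h, about 11%, 19% and 20% had an observed Tmax of 8 h or earlier and a negative slope, at 5%, 10% and 15% error. Their median T1/2 from the 16–24 h pair was about 25 to 27 h.

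**The case against.** A reader might infer that reported half-lives will be nearly double, or more than four times, the truth. The documents do not support that. The 13 h is a subcutaneous value. A Tmax near 12 h is an inference from two passages about the placebo check: the protocol ties that sample to Cmax, but the SAP gives only its purpose, to confirm that no liraglutide was received, and does not call 12 h the Tmax. Nothing in either document supports a Tmax of 16 h. If input from the joint ends by 16 h, the rule is unbiased. All of this stands, and it makes the multiples scenarios.

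Nor is the rule applied without exception, since a missing concentration or a non-negative slope blocks it. Neither exit catches a late peak followed by a fall, which is the case at issue.

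A reader might also extend the criticism to the other PK parameters. Cmax, Tmax and AUC0-t do not use λz, and SAP 13.3 already defines AUC0-t as running to the last quantifiable time, so no relabelling is needed there.

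The consequence is limited too. The secondary endpoint is plasma concentration, T1/2 is descriptive, and the DLT and stopping rules do not use it. Individual log-scale plots and concentration listings would let a careful reader see a segment that is not terminal. They do not correct the label or the summary table.

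**Conclusion.** The rule is wrong as written. It attaches a terminal label to a slope that nothing in the SAP requires to be terminal, and it accepts Cmax as one of its two points. That follows from the text and needs no model.

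The size is conditional. Under one compartment, first-order absorption and a 13 h elimination half-life, T1/2 comes out at about 14 h for Tmax 8 h, 23 h for 12 h (ratio 1.3 to 2.6 across the peaks that would be observed as 12 h) and 59 h for 16 h. A Tmax near 12 h is suggested but not stated, and 16 h is purely a scenario. The spread under assay error depends entirely on the precision assumed. The problem is confined to T1/2. It should be corrected, because the remedy is cheap and the value may be read as the first human half-life by this route.

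**What to change.** Amend SAP 13.3, with matching labels in 9.4 and the PK parameter table:

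- Keep the 16 h and 24 h points and the two existing conditions for a missing value.
- Report T1/2 as terminal only when observed Tmax is 8 h or earlier.
- When observed Tmax is 12 h, report the value separately as an apparent half-life over 16–24 h, not as an elimination half-life.
- When observed Tmax is 16 h or later, set T1/2 to missing.
- For each dose, state the number with an evaluable terminal T1/2 and the number excluded for late Tmax or for a non-negative slope.
- Do not add the 12 h point as a remedy for bias.

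This changes wording and programming only, with no new samples. Fewer participants will have a terminal half-life, possibly few or none at a dose where absorption is slow. The gate reduces the bias but does not remove it: with assay error some late absorbers will still show an early Tmax and pass. The table should carry a footnote saying so.
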